COVID-19 Information Seeking. Participants will be asked about the frequency (never, <1x/day, 2-4x/day, 5-8x/day, 9-16x/day, and >16x/day) of their interactions with various sources of information, including the news, social media, and interpersonal discussions about COVID-19 using a measure modified from other published studies. For analyses, interactions will be categorized as never, <1x/day, 2-4x/day, 5+x/day.

COVID-19 Worries. Participants will be asked to rate their overall level of worry about COVID-19 on a Likert Scale ranging from 1 for “not worried at all” to 4 for “very worried”. They will be then asked to endorse fifteen specific worries on a list developed for this study. Exploratory factor analyses will be conducted to identify domains within the questionnaire, with oblimin rotation on a tetrachoric correlation matrix due to the binary nature of the variables. Worries will be categorized into the following domains: social (parents/grandparents unable to visit, family unable to visit, not able to have a baby shower, not able to attend a funeral), COVID-19 infection-related (participant or partner will bring infection home, family or friends will get COVID-19), child-related (no adequate childcare, other children will get COVID-19), delivery-related (partner not present during delivery, changes to delivery plan, unborn baby will get COVID-19, not able to breastfeed), economic (significantly affect economic situation/finances), and missing doctor appointments.

COVID-19 prevention behaviors. Participants will be asked to endorse seventeen behaviors they had engaged in to protect themselves from COVID-19 from a list developed for this study based on WHO recommendations and media reports. Behaviors will be classified into the following categories: hygiene-related (mask-wearing, washing hands, disinfecting surfaces), physical distancing (avoiding public places, restaurants and other people, canceling personal engagements, work or school and

working at home), canceling travel (for work or pleasure), stockpiling essential resources (food or water, hand sanitizer, medication), postponing medical care, and prayer.

Mental Health Outcomes

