Standard socio-demographic measures will be collected including age, education (categorized as never attended school, elementary school, some high school, high school graduate or general equivalency diploma (GED), some college/university, college diploma or university degree, master's degree, professional degree, doctoral degree), self-identified race/ethnicity (categorized as White/Caucasian, Latina/Hispanic, Asian, South Asian, Black, Middle Eastern, Native Hawaiian or Other, Pacific Islander, American Indian or Alaska Native, Other/Multiracial), employment status (healthcare worker in a hospital or clinic, worked in a nursing home, essential/key worker (as defined by the government), none of these, don't know), medical coverage status, marital status (married, living with partner, divorced, separated, single, widowed), weeks pregnant/postpartum (first trimester 0 to <13 weeks, second trimester 13 to <28 weeks, third trimester 28+ weeks, postpartum). Participants indicated their country of residence which was classified by region for analytic purposes.

Statistical analyses

Descriptive statistics for socio-demographic characteristics, COVID-19 exposure variables, mental health, and loneliness will be calculated by perinatal stage, classified as first, second, or third trimester, or post-partum, for all participants. A series of multivariable logistic regressions will be then run to test the study hypotheses. For these analyses, PHQ-4, IES-6 and UCLA-3 outcomes will be specified as binary dependent variables using recommended cutoffs. The first set of models included pregnancy stage, socio-demographic variables and COVID-19 exposure as independent variables. The second set of models examined the type and amount of information seeking about COVID-19 as independent variables. The third and fourth set of models focused on COVID-19 worries and COVID-19 behaviors as independent variables. Models for information seeking, COVID-19 worries, and

COVID-19 behaviors will be adjusted for age, level of education, race, survey region, marital status, and pregnancy stage.

Models will be estimated using the GLM function in the R statistical program, version 3.6.2. Due to the number of models run, interpretations are focused on effects that met the threshold of $p < .001$. Due to low levels of missingness (667 [9%]) a complete case analysis was conducted. The raw data used for the study are publicly available.

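### The behavior models (set 4) omit the COVID-19 worry rating that the survey collects, so a behavior odds ratio can pass p < .001 while reflecting worry; report set 4 with and without it

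*SAP*

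**What the plan says.** The SAP, under Statistical analyses, plans four sets of multivariable logistic regressions. Of the last two it says: "The third and fourth set of models focused on COVID-19 worries and COVID-19 behaviors as independent variables". Read alone, this could mean both exposures in both sets. A later sentence on adjustment names the information-seeking, worry and behavior models separately, so the natural reading is worries in set 3 and behaviors in set 4. The adjustment list is closed: "COVID-19 behaviors will be adjusted for age, level of education, race, survey region, marital status, and pregnancy stage". It contains no worry variable.

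On the outcomes: "PHQ-4, IES-6 and UCLA-3 outcomes will be specified as binary dependent variables using recommended cutoffs". On the threshold: "interpretations are focused on effects that met the threshold of $p < .001". The reason given for it is "Due to the number of models run", that is, multiplicity.

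A measure of worry is in the data. Under COVID-19 Worries: "Participants will be asked to rate their overall level of worry about COVID-19 on a Likert Scale", with levels 1 to 4. Under COVID-19 prevention behaviors: "Participants will be asked to endorse seventeen behaviors they had engaged in to protect themselves from COVID-19". These are grouped into six categories.

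**The concern.** The behaviors are defined by a protective purpose, so concern about COVID-19 is a plausible motive for them. The outcomes lie close to worry as well: the PHQ-4 includes anxiety items, and the IES-6 statements are reworded to refer to the pandemic. Worry is therefore a plausible common cause that the survey measures and set 4 leaves out. The worry and behavior lists also overlap in content, since missed doctor appointments are a worry and postponed medical care is a behavior. Sets 3 and 4 could report one signal as two findings.

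At stake is how set 4 is read. Hygiene, distancing, stockpiling or prayer could be reported as associated with depression and anxiety, posttraumatic stress or loneliness, and readers could take that as something about the behavior. As planned, no model shows how far such a result depends on worry. The strict threshold limits chance findings; it does not limit bias, which persists as the sample grows.

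**Working it through.** The documents give no effect size or power figure to reproduce, so this is a sensitivity calculation.

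**Sample size.** The SAP says: "Due to low levels of missingness (667 [9%]) a complete case analysis was conducted". Then 667 / 0.09 = 7,411 responses, less 667 = 6,744 complete cases (6,354 to 7,180 if 9% is rounded from 9.5% or 8.5%). Protocol section 5.4 expects about 5,000 responses; 5,000 × 0.91 = 4,550.

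**Assumptions not in the documents.** Worry levels 1 to 4 in 8, 27, 40 and 25% of women; each behavior coded yes/no; a two-sided Wald test (critical z 3.29); true behavior odds ratio 1. The pairs of behavior and outcome prevalence are 50/30%, 20/40% and 90/40%. The six planned covariates are not simulated.

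**One case by formula.** With worry omitted, P(Y | B) = Σ P(w | B) P(Y | w). Take an odds ratio of 1.5 per worry level on both sides, behavior 50%, outcome 30%.
- P(B | w) = 0.323, 0.417, 0.518, 0.617; P(Y | w) = 0.166, 0.230, 0.310, 0.402.
- P(Y | B = 1) = 0.313 and P(Y | B = 0) = 0.287.
- Apparent odds ratio = (0.313/0.687) / (0.287/0.713) = 1.13; log = 0.124.
- With 3,372 women per group, SE = √(1/1,055 + 1/2,317 + 1/968 + 1/2,404) = 0.053, so the expected z is 2.33.
- Chance of passing = 1 − Φ(3.29 − 2.33) = 17%.

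The same steps at 2.0 on both sides give 0.335 against 0.265, odds ratio 1.39, z about 6.2, chance 99.8%. At 1.3 on both sides they give odds ratio 1.06, z 1.01, chance 1.1%.

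**Simulation.** 400 runs per scenario; ranges are over the three prevalence pairs; worry not in the model.

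| Worry OR per level: behavior / outcome | Apparent OR, n = 6,744 | p < .001, n = 6,744 | p < .001, n = 4,550 |
|---|---|---|---|
| 1.0 / 1.5 | 0.99–1.00 | 0% | 0% |
| 1.2 / 1.2 | 1.03 | 0.3–0.7% | 0–0.5% |
| 1.3 / 1.3 | 1.06–1.07 | 0.3–2.2% | 0.3–0.5% |
| 1.5 / 1.5 | 1.13–1.14 | 2.5–18.5% | 2–9% |
| 1.5 / 2.0 | 1.22–1.25 | 24–72% | 10–44% |
| 2.0 / 2.0 | 1.38–1.45 | 82–99.8% | 59–98% |

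With worry in the model, linear or as a factor, false findings fall to 0 to 0.5% in every scenario. For comparison, chance alone over 6 categories × 3 outcomes = 18 independent tests gives 1 − 0.999^18 = 1.8%.

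**Where adjustment misleads.** If behavior raises worry and worry raises the outcome, one illustrative case moves a total odds ratio of 1.16 to 1.00 on adjustment. If behavior and outcome are unrelated but both raise worry (behavior 50%, outcome 30%, n = 6,744), adjusting for worry creates an inverse association. With odds ratios on worry of 1.5 (behavior) and 2 (outcome) the null becomes about 0.92, passing p < .001 in about 4 to 6% of runs. With 2 and 2 it becomes about 0.87 (23 to 28%), and with 2 and 3 about 0.80 (67 to 73%). The ranges are over repeat simulations.

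**The case against.** The strongest case against is that confounding is plausible but not shown. The documents report no association of worry with behavior or with any outcome. The behavior list was drawn from WHO recommendations and media reports, and following public advice or working from home need not track individual worry. If worry and a behavior are unrelated there is no bias (first row of the table). A reader might infer that every set 4 odds ratio contains a worry effect. The documents do not support that. This objection stands, and it limits the point to what set 4 can show.

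The figures also depend on the inputs. The planned covariates, region for example, may absorb part of the shared variation. If six behaviors enter jointly at 1.5 on both sides, the apparent odds ratio per behavior is about 1.12 (9% pass) rather than about 1.14 (16%) when one is fitted alone. The chance that at least one of the six passes is then 43%, so the concern remains.

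A reader might also infer that the worry-adjusted model is the correct one and should replace the planned model or decide which behaviors may be called associated. The design does not support that. Protocol section 5.6 describes one cross-sectional survey, so the order of worry, behavior and symptoms is unobserved. Nor is the adjusted estimate merely conservative: the last calculation shows that it can create inverse findings. This part of the objection stands in full.

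Finally, Protocol section 16.1 plans a descriptive analysis and the SAP states no causal estimand for set 4. That lowers the stakes. But the SAP presents the regressions as tests of study hypotheses with adjustment, so readers will give the adjusted odds ratios more weight than a cross-tabulation.

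**Conclusion.** The omission is a matter of text: set 4 has no worry term, and the plan contains no analysis that shows what including one would do. The consequence is conditional. With moderate to strong links (odds ratios of about 1.5 to 2.0 per worry level on both sides), a behavior with no association of its own shows an apparent odds ratio of about 1.13 to 1.45. It passes p < .001 in anything from 2.5% to nearly all data sets at about 6,744 complete cases. With weak links (1.2 to 1.3) it would rarely pass. Which case applies cannot be told from the documents. The result rests on the assumed worry distribution, prevalences and links, on the inferred sample size, and on leaving the planned covariates out of the simulation.

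This does not invalidate set 4. It limits what set 4 can claim about behaviors independent of worry, and a side-by-side report would make that limit visible.

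**What to change.** Keep the planned set 4 models, with their six covariates, as primary. Then add to the SAP:
- a pre-specified sensitivity analysis that refits each set 4 model with the overall worry rating as a four-level factor;
- one table with the odds ratios and confidence intervals from both models side by side;
- a reporting rule that a behavior association which disappears on adjustment is not described as independent of worry;
- a statement that worry may be a confounder, a mediator or a consequence of behavior and symptoms in this survey, so the adjusted odds ratio can be over-corrected or biased below 1. The adjusted model therefore does not decide which associations are reported, and a new inverse association that appears only after adjustment needs the same caution.

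The cost is a few lines of SAP text and one extra fit per planned set 4 model: 3 if the behaviors enter jointly (one per outcome), or 6 × 3 = 18 if each category is fitted separately. The SAP does not say which is intended and should. No new data are needed.

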5.2. Does the study involve more than one participant group?

No **Yes:** *If yes, identify each group here and throughout all applicable sections.*

Pregnant women will be the only participants enrolled. No question will be asked about babies.

5.3. Indicate the duration of a participant’s involvement.

Participants will complete a single online survey (20 min approximately). There will be no follow up.

- 5.4. Indicate the total number of participants to be screened (if applicable) and/or enrolled (i.e., signed consent form). If the proposed research involves secondary data analyses only, indicate the number of data, documents, records, and/or specimens that will be obtained.**

We expect to receive responses from around 5000 women. If we launch quickly.

- 5.5. List inclusion and exclusion criteria, including age ranges of all participants, and describe the screening process.**

To be eligible for this study women must:

- (1) be 18 years of age or older,
- (2) self-identify as pregnant or recently pregnant (within the last 6 months),
- (3) be fluent in the English language, and
- (4) have access to a computer, tablet, or smartphone with an Internet connection.

The study population will consist of volunteers from any country in the world except European countries/those covered by GDPR.. It is expected that the Registry participants will represent a wide range of maternal age, race/ethnic background, and health status given the ubiquitous presence of smartphones and high-speed Internet connectivity among millennials (18 to 34 years of age) and Gen X (35 to 46 years of age).

Regarding the screening, when women click to participate in the Survey they will confirm the inclusion criteria above.

- 5.6. Describe study procedures.**

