Title: Health and Wellbeing of Pregnant and Post-Partum Women During the COVID-19 Pandemic

Document: Statistical Analysis Plan

NCT number: 04385238

Date: 04 May 2020

An anonymous, online, cross-sectional survey targeting pregnant and postpartum women will be conducted in 64 countries between May 26 2020 and June 13 2020. Participation in this study will be voluntary. All potential participants will be informed about the research objectives and standards of confidentiality regarding the use of the data. The survey, hosted on the Pregistryplatform for COVID-19 studies (<https://corona.pregistry.com>), will be advertised predominantly in social media channels and online parenting forums. Advertisements and the survey will be available in twelve languages (Arabic, Chinese, English, French, German, Italian, Korean, Portuguese, Russian, Spanish, Turkish, and Urdu) by human translators. We will seek to obtain at least 100 responses from each of the countries with the highest number of COVID-19 cases at the time of recruitment. Interested participants will be invited to follow a link to take the survey. The survey will collect standard demographic data and included questions that addressed topics such as COVID-19 exposure and worries, lifestyle changes, media exposure, protective factors, and mental health.

Participants. Women who self-identified as being 18 years or older at the time of the survey and as currently pregnant or having given birth within the past 6 months will be eligible to participate. The study was classified exempt by the Harvard Longwood Campus Institutional Review Board (HLC IRB) per the regulations found at 45 CFR 46.104(d)(2) on the basis that it poses no greater than minimal risk and that the recorded information cannot readily identify the subject (directly or indirectly).

Measures

COVID-19 Assessments

COVID-19 Exposure. Questions assessing whether participants were tested, diagnosed, or in contact with an individual who had COVID-19 will be adapted for this study based on those formulated by the US Centers for Disease Control and Prevention for the Household Pulse Survey.

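### A plain GLM with region as the only geographic term understates standard errors for region and country-patterned covariates if outcomes differ between countries within a region

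*SAP*

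**What the plan says.** The SAP's opening design paragraph says the survey "will be conducted in 64 countries between May 26 2020 and June 13 2020". Under Sociodemographic factors and potential confounders it adds: "Participants indicated their country of residence which was classified by region for analytic purposes".

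Under Statistical analyses, the binary PHQ-4, IES-6 and UCLA-3 outcomes go into four sets of multivariable logistic regressions:

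- Set 1: "The first set of models included pregnancy stage, socio-demographic variables and COVID-19 exposure as independent variables". No geographic term is named.
- Sets 2–4 (information seeking, worries, behaviours): these models, including those for "COVID-19 behaviors will be adjusted for age, level of education, race, survey region, marital status, and pregnancy stage".
- Estimation: "Models will be estimated using the GLM function in the R statistical program, version 3.6.2".
- Reading of results: because many models are run, "interpretations are focused on effects that met the threshold of" p<.001.

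Neither document mentions a country fixed or random effect, GEE, clustered or robust standard errors, or a sensitivity analysis by country. Protocol 16.1 is descriptive only. Protocol 2.2 mentions geographic differences as part of the study's significance, and no test of region is planned.

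**The concern.** R's `glm()` treats women as independent given the covariates in the model. If outcome prevalence differs between countries within a region, women from the same country remain correlated after adjustment for region. Region is constant within a country, so its standard error takes the full effect. Other covariates take it in proportion to how far their distribution differs by country.

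Two things are at stake.

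1. **Precision.** The p<.001 filter becomes looser than it looks for country-patterned covariates, and region terms, if read, look more certain than they are. A strict threshold gives no protection, because the relative inflation is larger far out in the tail.
2. **Confounding.** Country differences left inside a region can bias the coefficient of an individual-level covariate. Changing the standard error does not remove that.

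**Working it through.** The plan contains no design-effect or power figure to reproduce. As a calibration check, a design effect of 1 returns 2·(1−Φ(3.2905)) = 0.001. In simulation with no between-country variation, the plain GLM also behaves: true SD / reported SE is 0.97–1.01, and p<.001 occurs in 0.1–0.2% of studies.

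**Inputs from the documents**
- 64 countries (SAP design paragraph); threshold p<.001, taken as two-sided.
- Women per country: the SAP says "Due to low levels of missingness (667 [9%]) a complete case analysis was conducted". 667/0.09 = 7,411. If those 667 are the excluded cases, 7,411 − 667 = 6,744 and 6,744/64 = 105 (99–112 if 9% is rounded from 8.5–9.5%).
- Alternative from Protocol 5.4: "We expect to receive responses from around 5000 women", so 5,000/64 = 78.

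**Assumed, because the documents do not say:** outcome ICC 0.01, 0.02 or 0.05; 6 regions; prevalence 40%; spread of country sizes.

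**Step 1: region contrast, no true effect.** DEFF = 1 + (m − 1)·ICC; true error = 2·(1−Φ(3.2905/√DEFF)). With m = 105.4 and ICC 0.01, DEFF = 1 + 104.4 × 0.01 = 2.04 and √2.04 = 1.43.

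| ICC | DEFF | SE ratio (√DEFF) | Error, formula | Error, simulated, equal sizes | Error, simulated, unequal sizes (CV 0.94) | Error, formula, 5,000 women |
|---|---|---|---|---|---|---|
| 0.01 | 2.04 | 1.43 | 2.1% | 2.1% | 4.8% | 1.3% |
| 0.02 | 3.09 | 1.76 | 6.1% | 6.2% | 11.5% | 3.9% |
| 0.05 | 6.22 | 2.49 | 18.7% | 18% | 28% | 13.5% |

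The simulated columns use 20,000 studies per cell for equal sizes. A separate simulation, with the ICC on the latent logistic scale, prevalence about 38% and a different draw of unequal sizes, gave 3.2%, 7.3% and 22.7%. The direction is the same; the size depends on the scale of the ICC and on the spread of country sizes.

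**Step 2: individual-level covariates, no true effect.** DEFF = 1 + (m − 1)·ICC(outcome)·ICC(covariate). For covariate ICC 0.2 and outcome ICC 0.05, DEFF = 1 + 104.4 × 0.05 × 0.2 = 2.04, giving 2.1%. Simulated rates at p<.001, from a GLM with region plus the covariate (4,000 studies per cell):

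| Covariate's country ICC | Outcome ICC 0.01 | 0.02 | 0.05 |
|---|---|---|---|
| 0.5, equal sizes | 0.7% | 1.9% | 8.2% |
| 0.2, equal sizes | 0.2% | 0.5% | 2.2% |
| 0.2, unequal sizes | 0.4% | 0.9% | 3.9% |

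A covariate unrelated to country gave 0.05–0.2% throughout, which is nominal.

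**Step 3: confounding.** The setting is covariate ICC 0.2, no individual-level effect, country means of covariate and outcome correlated 0.3 to 0.5 within region, and equal sizes (1,500 studies per cell). The plain GLM reaches p<.001 in 1.4–7.5%, 5.5–21% and 24–63% of studies at outcome ICC 0.01, 0.02 and 0.05. Small-sample-corrected cluster-robust errors still give 0.8–22%; country fixed effects give 0–0.4%. A linear approximation of the same settings gives about 1–61% for the plain model, at most 1.3% with a country random intercept and at most 0.3% with country fixed effects.

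**Step 4: do the remedies work for region?** Error at p<.001 across all cells:

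| Method | Error |
|---|---|
| Random intercept, Wald z | 0.16–0.48% |
| Random intercept, t with 64 − 6 = 58 df | 0.04–0.32% |
| Cluster-robust, uncorrected | 0.46–1.56% |
| CR2 with Satterthwaite t | 0.02–0.27% |
| CR3 with Satterthwaite t | 0.005–0.14% |

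**The case against.** - **The largest figures concern a term that may not be read.** No regional test is planned, and region is an adjuster in sets 2–4. This stands as a point of emphasis. However, region is described among the socio-demographic factors, so it may well sit in set 1 as an independent variable; the SAP should say.
- **For the exposures in sets 2–4, the standard-error effect may be small.** At covariate ICC 0.05 and outcome ICC 0.02, DEFF = 1 + 104.4 × 0.02 × 0.05 = 1.10, which is close to nominal. Binary covariates with latent-scale ICCs also give lower rates than Step 2. This stands: the concern covers strongly country-patterned covariates, not every covariate.
- **The simulated model is leaner than the SAP's.** Race, education and marital status could absorb some country differences, so the ICC that matters is the residual one. This stands, and is a reason to read the results as a range.
- **The 5,000-woman figure mixes designs.** The protocol describes an English-language survey outside GDPR countries; the SAP describes twelve languages and 64 countries. This is fair: the 78 per country is only a smaller-sample comparison.
- **The 64 countries could be treated as fixed.** The standard-error point for region then weakens, but confounding by country within region remains.
- **The confounding figures rest on an assumed correlation of country means.** This is true; they show what is possible, not what is expected.
- **A mixed model is not better than CR2 or CR3 on error rate for region.** This is correct. The reason to prefer it is Step 3, where corrected clustered errors still leave up to 22%.

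**Conclusion.** The concern holds and should be fixed. Given any between-country variation within regions, the direction is certain: standard errors for region and strongly country-patterned covariates are too small when inference extends beyond these particular countries. The size is conditional. At about 105 women per country and ICC 0.01 to 0.05, a region contrast passes p<.001 under the null in roughly 2% to 18% of studies with equal country sizes, and more often with unequal sizes. A covariate with country ICC 0.2 does so in 0.2% to 2.2%. Covariates unrelated to country are at nominal. The confounding risk is separate and does not depend on whether countries are viewed as fixed or random. Every input other than the number of countries and the approximate sample size is an assumption, so confidence is high on direction and limited on magnitude.

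**What to change.** State in the SAP that:

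1. All four model sets are logistic mixed models with a random intercept for country of residence, with region a named fixed effect in every set, including set 1.
2. Region is tested against a t reference with degrees of freedom equal to countries minus regions.
3. If a model does not converge, country-clustered standard errors with a bias-reduced variance (CR2 or CR3) and a t reference are used, not uncorrected robust errors.
4. For individual-level covariates, a sensitivity analysis replaces region with country fixed effects, and the report lists which effects change sides of p<.001.

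The cost is SAP wording and a different R function, with no new data. Intervals for region and country-patterned variables will be wider. The fixed-effects analysis cannot estimate region and drops any country where all women have the same outcome.
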